7.3. Data Monitoring Plan

The monitoring plan for the Registry will involve routine (i.e., quarterly) monitoring by the PI and/or designees to ensure 1) direct participant identifiers are not contained within the Registry; 2) MPN Research Foundation investigator exports from the Registry are documented; 3) information linking the Registry linkage codes with participant identifiers is stored securely and access to the linkage code key is audited; and 4) any conditions that may negatively impact the confidentiality of information contained within the Registry are reported to the appropriate MPN Research Foundation personnel.

As specified previously, the DAUP Committee must provide approval for an MPN Research Foundation investigator to access the Registry for research studies involving the use of study Data. Access by MPN Research Foundation investigators to the Data for the purpose of identifying potential participants for participation in a research study shall be granted only upon the provision of documentation that an IRB has approved the research study. At the time of annual IRB continuing review, a list of studies conducted using the Registry will be submitted to the IRB. In addition, any unauthorized access to information contained within the Registry or to the information linking the Registry information linkage codes to participant direct identifiers shall be reported to the IRB.

7.4. Research Methods

This study will implement a structured methodology encompassing data acquisition, curation, validation, and governance. Data will be sourced from:

- **EMRs:** Retrospective and prospective clinical data, including laboratory results, imaging studies, physician notes, and treatment history.
- **PROs:** Longitudinal symptom assessments, quality of life metrics, and functional status evaluations.
- **Genomic and Molecular Data:** Mutation profiles, variant allele frequencies, and emerging biomarkers relevant to disease evolution.
- **Administrative Claims Data:** Healthcare utilization patterns, insurance claims, and medication adherence metrics.

To ensure data consistency and quality, all collected data will be standardized using internationally recognized coding systems, such as ICD-10, SNOMED CT, LOINC, and the United States Core Data for Interoperability (USCDI). Rigorous data validation processes will be implemented, including:

- Automated and manual data quality checks.
- Cross-validation between EMRs and PROs.
- Real-time monitoring of data completeness and accuracy.
- Periodic external audits to ensure compliance with best practices.

A governance framework will be established to oversee ethical compliance, data security, and appropriate use of registry data for research and regulatory purposes. Adaptive protocols will be

incorporated, allowing for modifications based on emerging scientific discoveries, technological advancements, and stakeholder feedback.

The study team anticipates that the protocol may be amended over time based on findings from the feasibility phase, input from one or more of the governance committees, stakeholder feedback, or evolving scientific and operational priorities. Potential amendments may include the addition of sub-studies, optional biospecimen collection, adjustments to PRO schedules, or updates to data collection methods. All amendments will be submitted for IRB review and approval prior to implementation.

7.5. Withdrawal/Discontinuation

Participants may withdraw consent at any time by submitting a written request (such as a signed form, email, or letter) to the study team. A record of the withdrawal will be maintained for regulatory compliance. Data collected prior to withdrawal will remain in the Registry for approved research; no additional data will be collected unless the participant re-consents.

7.6 Patient-Reported Outcomes Collection

7.6.1 Overview

The Registry will incorporate PROs to assess disease burden, symptom severity, quality of life, mental health, fatigue, and healthcare access. PROs will complement clinical and molecular data collected through EMRs to provide a comprehensive analysis of disease progression and treatment impact from the patient perspective.

PRO collection will provide valuable RWE to:

- Assess the impact of disease and therapy on quality of life.
- Support clinical decision-making and future research.

Identify early indicators of disease progression and treatment response.

The estimated time to complete the full PRO battery is 8–10 minutes per assessment. Efforts will be made to streamline survey administration and minimize participant burden while ensuring comprehensive data collection.

7.6.2 Selected Patient-Reported Outcomes Measures

Validated instruments have been selected based on their established use in major MPN clinical trials, including COMFORT-I & II, JAKARTA, PERSIST-1 & 2, RESPONSE, and SIMPLIFY trials. These measures align with recommendations for RWE collection in chronic hematologic diseases.

| Category | Measure | Purpose | Estimated Completion Time |
|----------------|---|--|---------------------------|
| Symptom Burden | MPN-SAF Total Symptom Score (MPN-SAF TSS) | Assesses key MPN symptoms, including fatigue, pruritus, night sweats, bone pain, and early satiety | 5–7 minutes |

| Category | Measure | Purpose | Estimated Completion Time |
|-----------------|---|--|---------------------------|
| Global Change | PGI-S (Patient Global Impression of Severity) | Captures patient-perceived overall change in health status | <1 minute |
| Quality of Life | EORTC QLQ-C30 | Evaluates overall health-related quality of life, including functional status and symptom burden | 7–10 minutes |
| Mental Health | Modified PHQ-9 | Screens for depressive symptoms commonly observed in MPN patients. Modified version excludes Question 9, which asks about suicidal ideation. | 2–3 minutes |
| Fatigue | PROMIS Short Form v1.0 – Fatigue 8a | Assesses fatigue in MPN patients, specifically targeting the experience of fatigue and its impact on daily life | 5-10 minutes |

Special Procedures for modified PHQ-9 Monitoring

The Registry collects patient-reported depressive symptoms using the modified PHQ-9 instrument.. While the registry is a non-interventional, observational study and does not provide clinical care or psychiatric services, the following safeguards are in place to responsibly manage participant well-being:

- All participants will see a message alerting them to the potentially sensitive nature of the questions included in the modified PHQ-9 and reminding them that they may choose to skip any question and may choose to forego completion of the modified PHQ-9 at any time.
- All participants, regardless of modified PHQ-9 score, will immediately see a resource referral pop-up in the online portal upon survey completion. This pop-up provides national mental health and crisis support resources, including the 988 Suicide & Crisis Lifeline, Crisis Text Line, and other relevant support services.
- The informed consent form will clearly communicate these boundaries to participants, including that the registry team does not provide medical or mental health services and that participants are responsible for seeking professional care if they have concerns about their well-being.

7.6.3 Data Collection Schedule

Data collection will follow a structured schedule to balance scientific objectives with participant burden. PROs will be collected on a tiered schedule. MPN-SAF TSS and PGI-S will be collected every 3 months (quarterly) to track changes in symptom burden. EORTC QLQ-C30, modified PHQ-9, and PROMIS Short Form v1.0 – Fatigue 8a will be collected every 6 months (biannually) to assess quality of life, mood, overall health, and fatigue.

Participants will have up to 7 days to complete each survey after it is sent, supported by automated reminders. This approach is designed to maximize data completeness while minimizing burden.

Clinical and EMR data will be updated at the same biannual timepoints and as available through data linkages. Table 2 provides an overview of the assessment schedule, and the recommended completion windows are summarized below.

| Timepoint | Recommended Completion Window |
|--|-------------------------------|
| Baseline Assessments | 7 days |
| 3-Monthly and Quarterly Follow-Ups (MPN-SAF TSS + PGI-S) | 7 days |
| 6-Month and Biannual Follow-ups (All PROs + EMR) | 7 days |

Note: MPN-SAF TSS and PGI-S are assessed every 3 months (quarterly); EORTC QLQ-C30, modified PHQ-9, PROMIS Short Form v1.0 – Fatigue 8a, and EMR data are assessed every 6 months (biannually). All assessments have a 7-day completion window supported by automated reminders.

7.6.4 Data Integration and Analysis

Integration of PROs with clinical and molecular datasets follows established methodologies for multi-source data validation in observational hematology studies⁷⁻⁹.

Handling of Partial or Incomplete Responses

- If participants complete only a partial assessment, data from completed sections will be retained.
- Participants with consistently incomplete responses will be flagged for additional follow-up.
- A threshold (e.g., $\geq 50\%$ completion) may be used to determine whether a submission is valid for analysis.
- Participants who submit incomplete assessments will be encouraged to complete the missing sections within the established grace period.
- If the assessment remains incomplete after the grace period, responses will be retained as submitted, and trends will be monitored for persistent gaps in reporting.

Non-Digital Data Entry and Quality Control

- Non-digital submissions (phone-based or paper forms) will be transcribed into the registry's electronic database by designated study personnel.
- A quality control process will be implemented to minimize transcription errors.

Providing PROs to Participants and Clinicians

- Participants may request summary reports of their individual PRO trends, which will be available through the registry portal.
- Where applicable, these reports may also be integrated into EMRs for treating physicians to support shared decision-making.

PROs will be integrated with clinical and molecular data collected through EMRs to create a comprehensive real-world dataset. This will allow for the evaluation of:

- Longitudinal changes in symptom burden and quality of life.
- Associations between trends and disease progression markers.
- Treatment effectiveness and tolerability from the patient perspective.
- Barriers to accessing care and medication adherence.

In the future, an optional online dashboard may be developed to allow participants to view their own reported data alongside general, de-identified study summaries. This dashboard will be intended solely for informational purposes and will not provide medical advice, treatment recommendations, or individualized clinical interpretations. Participation in dashboard access will be entirely optional and will not affect participation in the main registry.

7.7 Study Sites and Coordinating Center

The Principal Investigator, [name], is based at Memorial Sloan Kettering Cancer Center (MSKCC), which serves as the IRB site of record. All study operations, including participant recruitment, informed consent management, data collection, data storage, and participant communications, are centrally coordinated and administered by the MPN Research Foundation, located in Chicago, Illinois. The MPN Research Foundation functions as the study coordinating center and administrative office. No other clinical sites or healthcare institutions are engaged in participant enrollment, study management, or data operations.

8. RISK/BENEFIT ASSESSMENT

8.1. Potential Risks

Participation in this Registry involves minimal risk. The primary risk is potential loss of confidentiality or unauthorized access to personal information. To minimize this risk, all personally identifiable information (PII) will be separated from clinical and survey data and securely managed by the Honest Broker. Each participant's data will be linked using a unique study identifier, stored separately from the research database.

Although all data will be de-identified and coded, there is a minimal risk of re-identification, particularly when linking with external registries. Only authorized investigators operating under approved data use agreements will have access to de-identified datasets.

Survey responses will be stored in a secure, HIPAA-compliant system, with access restricted to authorized study personnel. As a non-interventional, observational study, there are no foreseeable physical or psychological risks, and no investigational treatments or procedures are involved.

Because the study does not involve clinical interventions or investigational products, no compensation for injury is provided. Participants will not incur any direct costs. In the event of a data breach, institutional policies and applicable laws will be followed, including prompt notification to affected participants and IRB reporting.

8.2. Benefits

As this is a non-interventional, observational study, there are no direct benefits to participants in this registry. However, their contributions will advance understanding of MPNs, disease progression, treatment patterns, and patient-reported experiences. The data collected may inform

clinical decision-making, improve care standards, support therapeutic development, and contribute to public health and regulatory efforts.

As part of the engagement strategy, participants will be eligible for periodic drawings for \$50 gift cards, held twice per year for completing PROs and once per year for maintaining active enrollment. Winners will be randomly selected, and no additional steps are required beyond completing the associated activities. These drawings are intended to acknowledge participant time and effort without exerting undue influence or coercion, as described in the ICF.

Participants may also benefit indirectly through access to educational materials, aggregate study updates, and invitations to optional webinars or virtual events related to MPN research.

8.3. Protection of Human Participants

Coded participant data will be retained for at least 10 years after study closure or as required by institutional policy and applicable regulations.

All data collection, storage, and sharing procedures will comply with IRB, HIPAA, FDA, EMA, and national research guidelines. Access to de-identified data for secondary research will require approval from the Registry Steering Committee, DAUP Committee and the IRB, and all requests will be reviewed for ethical use and scientific merit.

This protocol has been reviewed and approved by a central IRB. Ongoing oversight will include annual continuing review and prompt reporting of any unanticipated problems or breaches.

Participation in the Registry is voluntary, and participants may withdraw at any time without penalty. Data collected prior to withdrawal will be retained in coded form and may continue to be used for approved research unless otherwise requested by the participant.

To protect privacy, all electronic data will be stored on encrypted, access-restricted servers. Physical records will be secured in locked facilities. All study staff will be trained in Good Clinical Practice (GCP), human subjects protections, and institutional data privacy procedures.

9. STATISTICAL CONSIDERATIONS

Patient data will come from multi-modal data sources, including academic and non-academic health centers, patient-consented access to medical records, validated survey instruments, and patient self-reports. A durable and sizeable cohort over several years will generate longitudinal data that can be used in studies to allow researchers to analyze data potentially pertinent to disease progression. This cohort will capture a sufficient number of relatively rare events, such as disease progression to blast-phase MPN. At the development stage, the cohort composition and subsequent estimates of the risk of progression are uncertain. The registry aims to enroll approximately 1500 patients within 3 years. Under this sample size assumption, we estimate statistical power to detect an association between various risk factors and progression, as detailed in Table 1

Table 1: Minimum Hazard Ratio (HR) needed for the risk marker with power of 80%, type-1 error 5%, and the assumption of progression of 50% during the follow-up period

| Sample Size\Prevalence of marker | 10% | 20% | 30% | 50% |
|----------------------------------|------|------|------|------|
| 1000 | 1.53 | 1.37 | 1.32 | 1.3 |
| 2000 | 1.35 | 1.25 | 1.22 | 1.2 |
| 3000 | 1.27 | 1.2 | 1.17 | 1.16 |
| 5000 | 1.2 | 1.15 | 1.13 | 1.12 |

We estimate that the initial run-in part of a study duration will be at least 3 years. After 3 years, a statistical team will review the data and define a statistical analysis plan (SAP) based on the composition and completeness of the data.

Based on experience from similar projects in the past, we estimate an annual drop-out rate of 10-20%. As patients will enroll in this study on an ongoing basis, patients lost to follow up will be replaced over time to maintain adequate statistical power as illustrated in Table 1.

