9.1 Statistical Analysis Plan (SAP)

An initial SAP will be developed prior to data collection, outlining intended descriptive and inferential statistical methods, including Kaplan-Meier survival analysis²⁶, Cox proportional hazards modeling²⁷ for progression events, and multivariate analyses. Primary endpoints include time to documented MPN progression events and overall survival. Secondary endpoints include PROs, quality-of-life measures (e.g., EORTC QLQ-C30), and healthcare utilization patterns. Overall survival and cause-specific mortality endpoints will be determined using EMR data and validated through linkage with national mortality datasets, ensuring robust and comprehensive survival analyses. The SAP will undergo formal annual reviews and be updated based on interim analysis results, changes in data availability, or emerging scientific questions. Significant amendments will be documented, scientifically justified, and communicated to the IRB. Data will be securely retained for a minimum of 10 years following study completion, in accordance with institutional policies and regulatory requirements.

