9.2 Interim Analyses and Data Monitoring

Interim analyses will be conducted annually to evaluate data completeness, quality, and preliminary outcomes. These analyses will be reviewed by the Steering Committee and DAUP Committee, who will advise on data integrity, patient safety, and protocol compliance. Criteria triggering protocol amendments or corrective actions, such as enrollment targets or data quality thresholds, will be generally defined in the SAP. Corrective actions may include targeted data validation audits, protocol amendments, re-training of staff, or adjustments to participant follow-up procedures. Protocol deviations or violations identified during interim analyses will be documented, categorized, and reported to the IRB. Systematic issues leading to protocol deviations will trigger corrective actions.

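### Protocol Sections 9 and 9.1 time the SAP differently without saying which version governs, and 9.1 with 9.2 lets outcome results change it

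*Protocol*

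**What the plan says.** Four statements in the protocol bear on when the SAP is written and what may change it.

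- Section 9, after the sample size table: "After 3 years, a statistical team will review the data and define a statistical analysis plan (SAP". The sentence goes on to tie this step to how the cohort is made up and how complete its records are.
- Section 9.1: "An initial SAP will be developed prior to data collection, outlining intended descriptive and inferential statistical methods". The same section names two primary endpoints (time to documented progression, and overall survival) and the core methods (Kaplan-Meier, Cox).
- Section 9.1, on later changes: "The SAP will undergo formal annual reviews and be updated based on interim analysis results, changes in data availability, or emerging scientific questions". The safeguard is that "Significant amendments will be documented, scientifically justified, and communicated to the IRB".
- Section 9.2: "Interim analyses will be conducted annually to evaluate data completeness, quality, and preliminary outcomes".

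Section 6.1 also schedules an interim outcome assessment at Year 3, the point at which Section 9 has the SAP defined. Section 9.4 promises adjustment for multiple comparisons and leaves the method to the SAP.

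**The concern.** There are two separate problems.

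The first is timing. Section 9 speaks of defining a SAP at year 3 and mentions no earlier one. Section 9.1 has one in place before data collection and mentions no year-3 step. A reader cannot tell which document fixes the primary analyses, or when it stops changing.

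The second is what may change the plan. Under 9.1 interim results are an express ground for updating the SAP, and under 9.2 those results include outcomes. If they show how markers or treatments relate to progression or survival, the people revising the plan can see which definition, model or marker set looks favourable before they fix it.

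This matters because the registry is meant to do more than describe. Section 4.1 wants surrogate endpoints aligned with regulatory standards, and Section 6.3.4 wants data fit for regulatory submission. Table 1 is planned at a 5% type I error. An analysis chosen after its result was visible cannot be called pre-specified, and its nominal 5% does not hold.

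**Working it through.** **Step 1. The timing statements side by side.** Section 9: review after three years, then define the SAP, on composition and completeness. Section 9.1: initial SAP before data collection, then annual review and updating. The word initial in 9.1 allows a two-version reading (early SAP, fuller SAP at year 3). Even so, no section says that the year-3 document supersedes the initial one, which of them governs the primary analyses, or when the governing version is final.

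**Step 2. The route by which outcomes reach the SAP.** The Section 9 sentence alone does not supply it, because it is limited to composition and completeness. The route is 9.2 (annual results include preliminary outcomes) followed by 9.1 (interim results may change the SAP). Section 6.1 adds an outcome assessment at Year 3. Nothing in these sections confines the outcomes to pooled counts.

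**Step 3. What the safeguards do.** Documentation and notice to the IRB make a change traceable. Bonferroni, Holm or false discovery rate adjustment under 9.4 corrects for the tests finally listed. Neither corrects for having chosen those tests after seeing results, and the 9.4 method sits in the same changeable SAP.

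**Step 4. What the plan's 5% means.** Inputs from Section 9 and Table 1: 80% power, 5% type I error, 50% progression, marker prevalence p, sample size N. Schoenfeld's formula at a two-sided 5% is

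HR = exp[(1.960 + 0.842) / √(0.5 × N × p × (1 − p))].

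For N = 1000 and p = 10%: √(0.5 × 1000 × 0.09) = √45 = 6.708; 2.802 / 6.708 = 0.418; HR = 1.518.

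| N = 1000 | 10% | 20% | 30% | 50% |
|---|---|---|---|---|
| Recomputed | 1.518 | 1.368 | 1.314 | 1.285 |
| Table 1 | 1.53 | 1.37 | 1.32 | 1.30 |

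The other rows agree similarly: over all 16 cells, power at the stated hazard ratios is 78.1% to 83.5%. A one-sided 5% does not fit (1.449 against 1.53 in the first cell). Table 1 is not in error. Its 5% is a two-sided level for one fixed marker test, with no allowance for data-driven choice.

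**Step 5. An illustration of size.** Assumptions, not from the protocol: no true effect on either of the two primary endpoints, independent test statistics, no adjustment, and one interim look at information fraction t. The endpoint with the larger interim |z| is kept and tested on all the data at |z| > 1.96. With A and B independent standard normal for each endpoint, the final statistic is √t × A + √(1 − t) × B for the chosen endpoint. Simulation with 400,000 runs gives:

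| t | 0.3 | 0.5 | 0.7 | 1.0 |
|---|---|---|---|---|
| False positive rate | 7.0% | 8.2% | 9.0% | 9.7% |

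As a check, at t = 1 the exact value is 1 − 0.95² = 9.75%. If the statistics are positively correlated, as progression and death may be, the rate moves back toward 5%. With more candidates it rises: the best of four gives 9.9% to 18.6% over the same range of t.

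**The case against.** The strongest reply is that the protocol is better than its loosest sentence. Much of that reply stands.

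- The year-3 review is limited to composition and completeness. A reader might infer from Section 9 alone that the SAP is written around three years of outcomes. The text does not say so; that exposure comes only from 9.1 with 9.2.
- An initial SAP followed by a fuller one is a coherent plan. What remains open is which version governs.
- The primary endpoints and core methods are already named, so the analysis is not a blank slate. Component definitions, models and marker sets still can change.
- A reader might infer that type I error is left wholly unprotected. That goes too far: 9.4 promises control, 9.8 version-controls the scripts, and Sections 4.1 and 4.3 plan validation in external registries, which is a real check on data-driven findings. None of these fixes the primary analysis before its results are seen.
- A reader might also read the annual interims as repeated tests. Five or ten equally spaced looks at an unadjusted 5% would give about 14% or 19%. Section 9.2 describes no formal test and no declaration of success at a look, so those figures do not measure this plan.
- Detail may properly sit in a SAP that is not at hand. But the point does not rest on missing SAP detail. The protocol itself sets the SAP's timing and the grounds for changing it.

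**Conclusion.** The concern holds in two parts. Sections 9 and 9.1 need to be reconciled, because they do not say which SAP governs the primary analyses. And 9.1 with 9.2 expressly permits the SAP to be changed on outcome results, which neither notice to the IRB nor the adjustment in 9.4 corrects.

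The size is illustrative only. About 7% to 10% instead of 5% applies to a choice between the two named primary endpoints at one look, under the assumptions in the working. The protocol gives no number of candidate analyses, no information fractions and no number of confirmatory tests, so no figure can be called the plan's actual error rate. Table 1 stands as calculated. The matter is best settled before association results are seen, since pre-specification cannot be restored afterwards for the same data.

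**What to change.** 1. **Section 9.** Say that the year-3 step updates the initial SAP using only composition and completeness data, without marker-by-outcome or treatment-by-outcome results. State that this updated version governs the primary analyses and is final before any such association analysis is run. Tying the freeze to the first association analysis, not to the first data extraction, suits a registry that takes in historical records.
2. **Section 9.1.** Limit interim results as a reason for change to completeness, quality and pooled event counts. Removing them altogether would block sensible updates prompted by data quality.
3. **Sections 9.2 and 6.1.** For consistency, keep interim outcome summaries pooled until the governing SAP is final, and place any association work in the Year 3 assessment after that point.
4. **Later changes.** Label any change prompted by outcome associations as exploratory, or test it only on events accrued after the change or in an external registry.

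The cost is wording in the protocol and SAP, and less freedom to redefine primary analyses after year 3. Surrogate development in Stage 2 can continue as exploratory work with separate validation.
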